7.5 Efficacy Analyses

All efficacy analyses will be based on the Safety Population. Disease progression as collected at the end of treatment (end of study visit) as determined by the investigator will be used for the analysis for PFS, TTP, and DOR.

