10.3.2 EFFICACY ANALYSIS

An estimate of the ORR and its 1-sided 95% exact binomial confidence interval for the recommended Phase 2 dose group(s) will be determined. Additionally, the ORR and CBR along with the associated 2-sided 95% exact binomial confidence intervals will be determined for each dose cohort (within each schedule), including the recommended Phase 2 dose group (dose-escalation cohort + Phase 2 cohort). Responses will be defined using the IMWG-URC for sCR, CR, VGPR, or PR, and the EBMT for MR and nCR.

Analysis for time-to-events endpoints (PFS, DOR, and TTP) will be performed using the Kaplan-Meier method. Medians and other quartiles for each time-to-event endpoints will be estimated with the corresponding 2-sided 95% confidence intervals.

For purposes of calculating PFS, the start date for PD is the date at which progression is first observed. For such subjects, the primary analysis of PFS and DOR will be right-censored according to the conventions described in [Table 13](#). The same censoring rules, except for death, as in analysis of PFS will be applied in calculation of TTP. Subjects who die prior to progressive disease will be censored at the date of last evaluable response assessment.

Table 13: Date of Progression or Censoring for Duration of Response and Progression Free Survival

Situation	Date of Progression or Censoring	Outcome
No baseline disease assessments	Date of first dose	Censored
New anticancer therapy started before documentation of PD or death	Date of last disease assessment prior to start of new anticancer therapy	Censored
Death or PD immediately after more than 1 consecutively missed disease assessment visit	Date of last disease assessment visit without documentation of PD that is before the first missed visit	Censored
Alive and without PD documentation	Date of last disease assessment	Censored
Death or PD between planned disease assessments	Date of death or first disease assessment showing PD, whichever occurs first	Progressed
Death before first disease assessment	Date of death	Progressed

PD = progressive disease.

The mean, standard deviation, median, minimum, and maximum will be calculated for time to response (TTR).

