7.5.2 Progression Free Survival

Progression free survival (PFS) is defined as number of months (one month = 30.4 days) between start of treatment and first evidence of documented disease progression or death (due to any cause), whichever occurs first. Disease progression will be determined using IMWG-URC and will be determined by the investigator.

$$PFS = \text{Earliest date of disease progression, death, or censoring} - \text{Date of first dose} + 1 \text{ and expressed in months}$$

The duration of PFS will be right-censored for subjects who meet 1 of the following conditions: 1) starting a new anticancer therapy before documentation of disease progression or death; 2) death or disease progression immediately after more than 1 consecutively missed disease assessment visit or; 3) alive without documentation of

disease progression before the data cutoff date. For such subjects, the analysis of PFS will be right-censored according to the conventions described in Table 1.

Table 1: Date of Progression or Censoring for PFS and DOR

Situation	Date of Progression or Censoring	Outcome
No baseline disease assessments	Date of first dose	Censored
New anticancer therapy started before documentation of PD or death	Date of last disease assessment prior to start of new anticancer therapy	Censored
Death or PD immediately after more than 1 consecutively missed disease assessment visit	Date of last disease assessment visit without documentation of PD that is before the first missed visit	Censored
Alive and without PD documentation	Date of last disease assessment	Censored
Death or PD between planned disease assessments	Date of death or first disease assessment showing PD, whichever occurs first	Progressed
Death before first disease assessment	Date of death	Progressed

PD = progressive disease

Kaplan-Meier method will be used to estimate the distribution of PFS and the median and other quartiles in addition to the corresponding two-sided 95% confidence intervals.

Duration of follow-up for PFS will be summarized according to the Kaplan-Meier estimate of potential follow-up also termed “reverse Kaplan-Meier” (Schemper 1996).

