7.5.3 Time to Progression

Time to progression (TTP) is defined as number of months between start of treatment to the first documentation of disease progression. Disease progression will be determined using IMWG-URC as assessed by the investigator:

$$TTP = \text{Earliest date of disease progression or censoring} - \text{Date of first dose} + 1$$

and expressed in months

The same censoring rules, except for death, as in analysis of PFS will be applied in calculation of TTP. Subjects who die prior to progressive disease will be censored at the date of last evaluable response assessment.

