7.5.4 Duration of Response

Duration of response (DOR) will be calculated for subjects who achieve a sCR, CR, nCR, VGPR, or PR. For such subjects, the duration of overall response is defined as the time from first evidence of PR or better to disease progression or death due to any cause.

DOR = Earliest date of disease progression, death, or censoring - Date of first observation of PR or better before confirmation + 1 and expressed in months

Duration of response will be right-censored for subjects who at least achieve a PR based on the censoring conventions defined previously for PFS. Analysis of DOR will be performed using the Kaplan-Meier method. Medians and other quartiles for DOR will be estimated in addition to the corresponding 2-sided 95% confidence intervals.

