7.5.5 Duration of Clinical Benefit Response

Duration of clinical benefit response (CBR) will be calculated for subjects who achieve a MR or better. For such subjects, the duration of CBR is defined as the time from first documentation of MR or better to disease progression or death due to any cause. Dates of progression and censoring will be determined as described for the analysis of PFS.

Duration of CBR = Earliest date of disease progression, death, or censoring - Date of first observation of MR or better before confirmation + 1 and expressed in months

The duration of CBR will be summarized descriptively using the Kaplan-Meier method. The quartiles of the Kaplan-Meier distribution will be used to estimate the median duration of CBR.

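### SAP 7.5 takes progression for PFS, TTP and DOR from the end-of-study visit, whereas SAP 7.5.2, 7.5.3, Table 1 and protocol 10.3.2 use the first documented progression with no visit limit

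*SAP*

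**What the plan says.** SAP 7.5 opens the efficacy section with the analysis population and then the source of progression (PD) for PFS, TTP and DOR: "Disease progression as collected at the end of treatment (end of study visit) as determined by the investigator will be used for the analysis". Protocol 7.7 requires end-of-study assessments within 30 days of the last dose and before any other treatment.

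The sections that define the endpoints carry no such limit:

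- SAP 7.5.2 ends PFS at the "first evidence of documented disease progression or death (due to any cause), whichever occurs first". Its third censoring condition applies to a subject alive without documented "disease progression before the data cutoff date".
- SAP Table 1 dates an event between planned assessments as "Date of death or first disease assessment showing PD, whichever occurs first".
- SAP 7.5.3 defines TTP as the "number of months between start of treatment to the first documentation of disease progression".
- SAP 7.5.4 defines DOR as the "time from first evidence of PR or better to disease progression or death due to any cause".
- SAP 7.5.5, on duration of clinical benefit response, says: "Dates of progression and censoring will be determined as described for the analysis of PFS".
- Protocol 10.3.2 says that "the start date for PD is the date at which progression is first observed", and protocol Table 13 matches SAP Table 1.

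SAP section 1 ties the SAP to Amendment 3 and undertakes to identify any departure from the protocol's planned analyses. It declares none here.

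**The concern.** A record limited to the end-of-study visit cannot hold PD found later, and the protocol version behind the SAP expected some PD to be found later. Under Amendment 3, subjects who stopped for reasons other than PD were assessed every 8 weeks until PD or new myeloma therapy. Appendix N preserves that wording, and it is cited here only to show which follow-up applied. The current Appendix E still has an 8-weekly long-term follow-up column for subjects without PD, and its footnote i allows the progression sample to be taken in that follow-up.

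Two programmers working from the same SAP could therefore give such a subject different event indicators and dates. One would follow 7.5 and find no event; the other would follow 7.5.2, 7.5.3 and Table 1 and count one. If stopping is related to prognosis, dropping the later PD also makes the censoring informative.

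**Working it through.** **No planned figure to reproduce.** The documents state no median, event count or power for PFS, TTP or DOR. The only sized endpoint is ORR. Its figure reproduces (exact binomial, n = 46, reject at 12 or more responders: power 76.7% against the stated 77%, one-sided alpha 3.5%), and it does not use the PD date.

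**Timing, from the documents' intervals.**

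- The end-of-study window closes 30 days after the last dose (protocol 7.7).
- Follow-up was every 8 weeks = 56 days. The documents do not say where the 8 weeks start.
- Counted from the last dose, the first follow-up is on day 56, which is 56 − 30 = 26 days after the window closes.
- Counted from an end-of-study visit on days 0 to 30, it is on days 56 to 86, which is 26 to 56 days after the window closes.

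On either count, PD first found at a scheduled follow-up visit cannot be in the end-of-study record.

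**One hypothetical subject** (2/7 schedule, no delays, 8 weeks counted from the last dose).

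- Last dose on Cycle 6 Day 9: 5 × 14 + 9 = Study Day 79.
- End-of-study visit on the last permitted day: 79 + 30 = Day 109, no PD.
- PD first observed at follow-up: 79 + 56 = Day 135. Assume it is then confirmed, before any new therapy, by the second consecutive assessment that Appendix H requires for PD based on M-protein, free light chain or hypercalcemia.
- SAP 7.5.2 counts days from first dose plus 1 and divides by 30.4.

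| Rule | PFS and TTP outcome |
|---|---|
| SAP 7.5.2, 7.5.3 and Table 1 | Event at 135/30.4 = 4.44 months |
| SAP 7.5 literally, follow-up visits not counted as assessments | Censored at 109/30.4 = 3.59 months |
| SAP 7.5 literally, follow-up visits counted as assessments | Censored at 135/30.4 = 4.44 months |

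The event disappears in both literal versions. The SAP does not say which censoring date applies. For PFS, a later death could still count, subject to the Table 1 rules on new therapy and missed visits.

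**Dependence on unknowns.** The inputs here are assumptions, not document figures: exponential times, true median time to PD 6 months, 24-month cutoff, no deaths, no new therapy, 200,000 simulated subjects, and literal censoring at the stop date.

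| Share stopping without PD | PD hazard after stopping | Median, follow-up PD counted | Median, 7.5 literally |
|---|---|---|---|
| 10%, 20%, 30%, 40% | unchanged | 5.97, 5.98, 6.01, 5.99 | 5.96, 5.98, 6.01, 5.99 |
| 10%, 20%, 30%, 40% | doubled | 5.83, 5.63, 5.45, 5.21 | 6.00, 6.00, 6.03, 5.99 |

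With an unchanged hazard the medians agree. With a doubled hazard the literal rule gives the longer median; by the same reasoning a lower hazard would work the other way. If censoring is instead at the follow-up visit itself, replacing an event by a censored time on the same date can only raise the Kaplan-Meier curve or leave it unchanged. The documents do not say which case applies.

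**The case against.** The strongest reply is that SAP 7.5 only says where the investigator's PD determination is recorded, and that 7.5.2 to 7.5.5 and Table 1 then govern events and dates. On that reading nothing conflicts and no change from the protocol needs declaring. The superseded Amendment 3 text gives some support: it said that confirmed PD at a disease assessment need not be re-established at the end-of-study assessments, which fits the end-of-study record being a reporting place. This reading is possible, and it is why the point is put conditionally. But the SAP does not state it, and a form completed at the end of treatment would still lack later PD unless it was updated.

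A second reply is that post-treatment assessments are no longer required. That is true under Amendment 4, but Amendment 4 followed completion of the primary analysis, and the SAP is written to Amendment 3.

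Two stronger readings are tempting and are not supported. A reader might infer that PFS and TTP will be overstated. The documents give no rate of stopping without PD, of later PD or of new therapy for this trial, and with censoring at the stop date and an unchanged hazard the effect is nil. A reader might also infer that TTP as a whole is compromised. It is not: PD on treatment or at end of study is captured under either rule, and only subjects who stop without PD and then progress before new therapy can differ.

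**Conclusion.** The inconsistency is in the current text and holds in a limited form. Taken literally, SAP 7.5 omits PD first documented in post-treatment follow-up, while SAP 7.5.2, 7.5.3, Table 1 and protocol 10.3.2 would count it. For the subjects concerned, the PD event is lost for TTP. For PFS, DOR and duration of clinical benefit response it is lost unless a death is counted instead.

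This rests on the literal reading of 7.5 and on the Amendment 3 follow-up having been carried out. The worked subject shows how the rules diverge for one person and says nothing about the trial's results; the size and direction of any effect on the estimates cannot be determined. These are secondary, descriptive endpoints with no test attached, and ORR is unaffected. Severity is low.

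**What to change.** Replace the second sentence of SAP 7.5 with:

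*PD is the first investigator-determined IMWG-URC PD (confirmed where Appendix H requires it) documented at any disease assessment, on treatment, at end of study or in post-treatment follow-up, up to the data cutoff and before new anticancer therapy; PD and censoring dates follow Table 1 using the same set of assessments.*

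Apply it to PFS, TTP, DOR and duration of clinical benefit response. If 7.5 was meant only to name a recording form, say so. If an end-of-treatment-only source was intended, declare it as a change from protocol 10.3.2 and align SAP 7.5.2, 7.5.3 and Table 1 with it. Where the analysis has already been run, the report should state which rule was used.

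The cost is one SAP sentence and minor derivation work. The reported estimates may move in either direction or not at all.

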7.5.1 Overall Response Rate

The overall response rate (ORR) is defined as proportion of subjects for whom the best overall confirmed response is stringent complete response (sCR), complete response (CR), near complete response (nCR), very good partial response (vGPR), or partial response (PR) as defined by International Myeloma Working Group Uniform Response Criteria (IMWG-URC) and modified European Group for Blood and Marrow Transplantation (EBMT) criteria (nCR). An estimate of the ORR and its 1-sided 95% exact binomial confidence interval for each of the recommended dose groups will be determined. Additionally, the ORR and CBR along with the associated 2-sided 95% exact binomial confidence intervals will be determined including the recommended dose group (dose escalation cohort + Phase 2 cohort).

7.5.2 Progression Free Survival

Progression free survival (PFS) is defined as number of months (one month = 30.4 days) between start of treatment and first evidence of documented disease progression or death (due to any cause), whichever occurs first. Disease progression will be determined using IMWG-URC and will be determined by the investigator.

$$PFS = \text{Earliest date of disease progression, death, or censoring} - \text{Date of first dose} + 1 \text{ and expressed in months}$$

The duration of PFS will be right-censored for subjects who meet 1 of the following conditions: 1) starting a new anticancer therapy before documentation of disease progression or death; 2) death or disease progression immediately after more than 1 consecutively missed disease assessment visit or; 3) alive without documentation of

disease progression before the data cutoff date. For such subjects, the analysis of PFS will be right-censored according to the conventions described in Table 1.

Table 1: Date of Progression or Censoring for PFS and DOR

Situation	Date of Progression or Censoring	Outcome
No baseline disease assessments	Date of first dose	Censored
New anticancer therapy started before documentation of PD or death	Date of last disease assessment prior to start of new anticancer therapy	Censored
Death or PD immediately after more than 1 consecutively missed disease assessment visit	Date of last disease assessment visit without documentation of PD that is before the first missed visit	Censored
Alive and without PD documentation	Date of last disease assessment	Censored
Death or PD between planned disease assessments	Date of death or first disease assessment showing PD, whichever occurs first	Progressed
Death before first disease assessment	Date of death	Progressed

PD = progressive disease

Kaplan-Meier method will be used to estimate the distribution of PFS and the median and other quartiles in addition to the corresponding two-sided 95% confidence intervals.

Duration of follow-up for PFS will be summarized according to the Kaplan-Meier estimate of potential follow-up also termed “reverse Kaplan-Meier” (Schemper 1996).

7.5.3 Time to Progression

Time to progression (TTP) is defined as number of months between start of treatment to the first documentation of disease progression. Disease progression will be determined using IMWG-URC as assessed by the investigator:

$$TTP = \text{Earliest date of disease progression or censoring} - \text{Date of first dose} + 1$$

and expressed in months

The same censoring rules, except for death, as in analysis of PFS will be applied in calculation of TTP. Subjects who die prior to progressive disease will be censored at the date of last evaluable response assessment.

7.5.4 Duration of Response

Duration of response (DOR) will be calculated for subjects who achieve a sCR, CR, nCR, VGPR, or PR. For such subjects, the duration of overall response is defined as the time from first evidence of PR or better to disease progression or death due to any cause.

DOR = Earliest date of disease progression, death, or censoring - Date of first observation of PR or better before confirmation + 1 and expressed in months

Duration of response will be right-censored for subjects who at least achieve a PR based on the censoring conventions defined previously for PFS. Analysis of DOR will be performed using the Kaplan-Meier method. Medians and other quartiles for DOR will be estimated in addition to the corresponding 2-sided 95% confidence intervals.

7.5.5 Duration of Clinical Benefit Response

Duration of clinical benefit response (CBR) will be calculated for subjects who achieve a MR or better. For such subjects, the duration of CBR is defined as the time from first documentation of MR or better to disease progression or death due to any cause. Dates of progression and censoring will be determined as described for the analysis of PFS.

Duration of CBR = Earliest date of disease progression, death, or censoring - Date of first observation of MR or better before confirmation + 1 and expressed in months

The duration of CBR will be summarized descriptively using the Kaplan-Meier method. The quartiles of the Kaplan-Meier distribution will be used to estimate the median duration of CBR.

7.6 Safety Analysis

All safety analyses will be based on the Safety population.

7.6.1 Adverse Events

Each reported AE term will be mapped to a preferred term (PT) and a system organ class (SOC) using the Medical Dictionary for Regulatory Activities (MedDRA).

Treatment-emergent adverse events (TEAEs) are defined as AEs that start on or after the first day of study treatment and within 30 days of the last day of study treatment. An AE that is present before the first administration of study treatment and subsequently worsens in severity during treatment is also considered to be treatment-emergent.

Adverse events will be summarized based on the number (%) of subjects experiencing events by MedDRA system organ class and preferred term. The denominator for the percentage will be based on the number of subjects at in the Safety Population (i.e., those that received at least one dose of study drug).

A subject reporting the same AE more than once will be counted only once when calculating 1) within a given system organ class, and 2) within a given system organ class and preferred term combination. For such cases, the maximum National Cancer Institute (NCI; US) - Common Terminology Criteria for Adverse Events toxicity grade and strongest causal relationship to study treatment for the event will be used in the incidence calculations. AEs will also be summarized by severity and by relationship to study drug.

An overall summary of TEAEs will summarize the number (%) of subjects

- with at least one TEAE
- with at least one treatment-related TEAE, defined as related to OPZ or DEX
- with at least one grade 3 or higher TEAE
- with at least one treatment-related grade 3 or higher TEAE, either OPZ or DEX
- with at least one serious AE
- with TEAE leading to discontinuation of study drug, either OPZ or DEX
- with TEAE leading to discontinuation of OPZ

- who died within 30 days of last dose of study drug

Summaries of the following TEAEs will be provided by SOC and/ or PT unless otherwise noted:

- all TEAEs
- all TEAs (PT)
- TEAEs by maximum severity
- treatment-related adverse events (OPZ, DEX, and study drug [OPZ/DEX])
- serious TEAEs
- TEAEs that led to permanent discontinuation of study drug (OPZ, DEX and study drug [OPZ/DEX])

Summaries that are displayed by system organ class and preferred terms will be ordered by descending order of incidence of system organ class and preferred term within each system organ class for the total group. Summaries of TEAEs, treatment-related AEs will also be provided by descending order of incidence of preferred terms in the total group.

All AEs, including TEAEs, will be included in listings by subject.

Listings of AEs determined to be DLTs during the first cycle of Phase 1, serious AEs, and AEs leading to discontinuation of study drug will be provided.

A summary of the number of deaths and the cause of death, classified by deaths within 30 days of last dose of study drug and deaths more than 30 days after the last dose, will be provided.

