9. ADVERSE EVENTS

9.1 ADVERSE EVENTS DEFINITIONS

An AE is any untoward medical occurrence in a study subject administered an investigational product(s), regardless of the causal relationship with treatment.

An AE, therefore, can be any unfavorable and unintended sign (including laboratory finding), symptom, or disease temporally associated with participation in an investigational study, whether or not considered treatment related. In addition to new events, any increase in the severity or frequency of a preexisting condition that occurs after the subject signs a consent form for participation is considered an AE. This includes any side effect, injury, toxicity, or sensitivity reaction. All reported AEs will be coded using Medical Dictionary for Regulatory Activities (MedDRA).

Laboratory findings should not be recorded as AEs unless corrective action is required (e.g., transfusions, initiation of antibiotics or treatment regimens, hydration) or the event is deemed clinically significant by the treating physician.

Any condition, laboratory abnormality, or physical finding with an onset date prior to the subject signing consent for study participation is considered to be preexisting in nature and part of the subject’s medical history.

An unexpected AE is any AE, the specificity or severity of which is not consistent with the current Investigator’s Brochure (IB) or prescribing information for a marketed compound; or that adds significant information on specificity or severity of a known, already-documented AE. For example, an event more specific or more severe than described in the Investigator’s Brochure would be considered “unexpected.”

Whenever possible, the NCI-CTCAE (Version 4.03) should be used to describe the event and for assessing the severity of AEs ([National Cancer Institute 2010](#)). **The National Cancer Institute Common Terminology Criteria for Adverse Events does not use to the term “intermittent” and this term must not be used to describe AEs.** Any AEs representing a change in the NCI-CTCAE grade need to be reported on the AE eCRF. For AEs not adequately addressed in the NCI-CTCAE, the table below ([Table 12](#)) may be used.

Table 12: Adverse Event Severity Grades

Severity	Description
GRADE 1 - Mild	Asymptomatic or mild symptoms; clinical or diagnostic observations only; intervention not indicated
GRADE 2 - Moderate	Minimal, local or noninvasive intervention indicated; limiting age-appropriate instrumental ADL

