9.3 ADVERSE EVENTS REPORTING PROCEDURES

9.3.1 GENERAL PROCEDURES

All AEs (e.g., any new event or worsening in severity or frequency of a preexisting condition or laboratory finding) with an onset date after the subject signs consent for study participation must be promptly documented on the AE eCRF. Details of the event must include severity, relationship to study drug, duration, action taken, and outcome. Whenever possible, reporting specific diagnosis is preferred rather than individual signs or symptoms. Serious adverse events will be recorded on the AE eCRF *and* on the SAE reporting form (see [Section 9.5](#), Serious Adverse Event Reporting and Documentation Requirements).

All AEs occurring from the time that the subject signs the ICF and through 30 days after the last administered dose of study drug will be reported, regardless of whether new chemotherapy regimens are initiated. In addition, the investigator should report any AE that may occur after this time period that is believed to have a reasonable possibility of being associated with study drug. If a subject discontinues the study prior to receiving any study drug, AEs must be

captured until it is documented that the subject fails to enroll in the study.

All AEs that are considered related to study drug and all SAEs regardless of relationship to study drug must be followed to resolution or stabilization if improvement is not expected.

Adverse events that completely resolve and then recur should be recorded as new AEs. For subjects who complete the End-of-Study Assessment less than 30 days following their last dose of protocol-defined therapy, a follow-up of ongoing AEs should be attempted by telephone and documented in the subject's source file. Adverse events continuing at 30 days after the last dose of study drug should have a comment in the source file by the investigator that the event has stabilized or is not expected to improve.

The investigator is responsible for evaluating all AEs, obtaining supporting documents, and determining that documentation of the event is adequate. The investigator may delegate these duties to subinvestigators and must ensure that these subinvestigators are qualified to perform these duties under the supervision of the investigator and that they are listed on the FDA Form 1572.

9.3.2 *DISEASE PROGRESSION*

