10.3.3 SAFETY ANALYSIS

Safety and tolerability assessments will include extent of exposure to study treatment, AEs (including the DLT assessment period DLTs and SAEs), laboratory values, vital sign results, and ECGs. Safety data will be examined on an ongoing basis to ensure subject safety.

Extent of exposure to the study treatment will be summarized using descriptive statistics (n, mean, standard deviation, median, and range). Percent of subjects and number of cycles with dose holds and reductions will be calculated by treatment group.

Adverse events will be coded using MedDRA. Treatment-emergent AEs are defined as AEs occurring from the first dose of study treatment through 30 days after the last dose of study treatment. An AE that is present before the first administration of study treatment and subsequently worsens in severity between the first dose of study treatment and 30 days after the last dose of study treatment is also considered to be treatment emergent. Adverse events will be summarized by MedDRA system organ class and preferred term for the number and percentage of subjects who experienced the event. A subject reporting the same AE more than once will be counted only once when calculating (1) within a given system organ class and (2) within a given system organ class and preferred term combination. For such cases, the

maximum NCI-CTCAE toxicity grade and strongest causal relationship to study treatment for the event will be used in the incidence calculations. Treatment-emergent AEs will be tabulated to examine their frequency, severity, and relationship to study treatment. Additional summaries will be provided for SAEs and events resulting in the permanent discontinuation of treatment. All AEs will also be included in individual subject listings.

A listing of subjects who experience a DLT during the DLT assessment period of the dose- escalation portion will be generated along with the results associated with the PK/PDn parameters considered.

Laboratory parameters will be summarized using descriptive statistics and by postdose shifts relative to baseline. Vital sign results will also be summarized descriptively for each scheduled protocol time point. Changes will be calculated relative to the values collected at baseline, defined as the last assessment taken prior to the first dose of study drug on Day 1 of Cycle 1.

The analysis of the locally performed ECGs will involve descriptive statistics.

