1 INTRODUCTION

This statistical analysis plan (SAP) was prepared for an abbreviated clinical study report (aCSR) in accordance with Protocol ONX-2012-001, dated 26 June 2014 (amendment 3), and describes the analyses of data collected within the scope of the study. Any changes that are made to the planned analyses after the SAP is finalized, along with an explanation as to when and why they occurred, will be noted in the abbreviated clinical study report produced for the study. Any changes made to the planned analyses that are in the protocol will be identified and documented in this document.

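### The SAP drops the 30 days after last dose when deciding whether a worsened pre-treatment AE is treatment-emergent; the protocol includes them, and the SAP does not record the change

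*SAP*

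**What the plan says.** Both documents define treatment-emergent AEs in two parts: AEs that are new, and AEs present before first dose that then worsen.

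Protocol 10.3.3 uses the same window for both. New events are "AEs occurring from the first dose of study treatment through 30 days after the last dose of study treatment". A pre-existing AE qualifies if it "subsequently worsens in severity between the first dose of study treatment and 30 days after the last dose of study treatment".

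SAP 7.6.1 treats the two parts differently. New events are "AEs that start on or after the first day of study treatment and within 30 days of the last day of study treatment". A pre-existing AE qualifies only if it "subsequently worsens in severity during treatment is also considered to be treatment-emergent". The SAP does not define the treatment period so as to include the 30 days.

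On departures from the protocol, SAP Section 1 states: "Any changes made to the planned analyses that are in the protocol will be identified and documented in this document". No departure is noted for this definition.

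On data collection, protocol 9.3.1 has AEs from consent "through 30 days after the last administered dose of study drug will be reported". Protocol 9.1 adds: "Any AEs representing a change in the NCI-CTCAE grade need to be reported on the AE eCRF".

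**The concern.** The SAP sentence on new events spells out the 30-day extension and the next sentence, on worsening, does not. The natural reading is that the extension does not apply to worsening. A programmer following the SAP would then use a shorter window than the protocol specifies, with nothing to show whether that was a decision or a slip of wording.

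Safety and tolerability are primary in both phases, and the TEAE flag decides which AEs enter the summaries of all TEAEs, of treatment-related TEAEs, of grade 3 or higher TEAEs, of maximum severity and of serious TEAEs. A narrower window can only remove events from those tables. It also sits oddly with SAP 8.1, which resolves uncertain AE onset dates the other way, by classifying the AE as treatment-emergent.

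**Working it through.** The documents give no figure to reproduce. The check is a comparison of the texts, followed by asking which events fall in the gap.

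**1. The windows side by side.**

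| Type of event | Protocol 10.3.3 | SAP 7.6.1 |
|---|---|---|
| New AE | First dose to last dose + 30 days | First dose to last dose + 30 days |
| Worsening of an AE present before first dose | First dose to last dose + 30 days | On treatment only |

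The difference is (last dose + 30 days) − (last dose) = 30 days, for worsening only.

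**2. Does the protocol version explain it?** The SAP was written to Amendment 3 and the protocol supplied is Amendment 4. The Amendment 4 summary of changes (Appendix N) lists no change to Section 10.3.3, so the version gap does not appear to be the cause.

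**3. Which events are exposed?** Sort them by when the condition began.

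- *Before consent.* Protocol 9.1 treats the condition as medical history, and treats an increase in its severity or frequency after consent as an AE. Protocol 9.3.1 has such worsening documented on the AE form with an onset after consent. If the worsening comes within 30 days after last dose, the SAP's sentence on new events captures it. Not exposed.
- *On or after first dose.* Already treatment-emergent as a new event. Not exposed.
- *Between consent and first dose.* This is an AE present before first dose, so only the worsening sentence can bring it in. It is exposed if it did not worsen on treatment and first worsened in the 30 days after last dose.

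The exposed interval is short: Appendix E places screening at Days -14 to -1.

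**4. Does the recording rule close the gap?** Protocol 9.1 requires a grade change to be reported on the AE form. If that creates a new record with its own start date, the sentence on new events captures the worsening. If the original record is updated, it does not. The documents do not say which applies.

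**5. Size.** The number of subjects meeting all the conditions in step 3 is not given and cannot be derived. The arithmetic gives only the unit: one subject in a recommended-dose group of 46 is 1/46 = 2.2 percentage points on one line of a table, and only if that subject has no other qualifying occurrence of the same term, since subjects are counted once per term. This is not an estimate of the effect.

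**The case against.** The strongest reply is that the mismatch has almost no practical effect. Most conditions that patients bring into the trial predate consent, and their later worsening is a new AE under protocol 9.1 and 9.3.1. Grade changes must be reported, which may cover the remainder. Other outputs do not depend on the worsening sentence: SAP 7.6.1 lists all AEs by subject whether or not treatment-emergent, lists serious AEs, and tabulates deaths within and beyond 30 days of last dose; SAP 7.6.2 summarises post-baseline grade 3 or higher laboratory toxicities from the laboratory results. DLTs are assessed in Cycle 1 or Cycle 2 and are untouched.

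Nearly all of this stands, and it limits the point to AEs arising between consent and first dose. It does not remove the point. The texts differ, the SAP does not record the difference, and the rule that would close the gap (a new record for each grade change) is not stated.

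A reader might infer something stronger: that baseline cytopenia, neuropathy or fatigue worsening in the month after treatment would be missing from every TEAE table, so that the events most typical of a relapsed population are undercounted. The documents do not support that. Such conditions usually predate consent, and their worsening then enters as a new AE.

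**Conclusion.** The discrepancy is real and undocumented, and the SAP wording should be brought into line with the protocol. Its reach is narrow: AEs that began between consent and first dose and first worsened in the 30 days after last dose could be left out of the TEAE summaries. Any error is an undercount, of unknown size and probably small.

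This rests on two assumptions: that the SAP phrase is applied literally, and that a grade change is not entered as a new AE record. If either fails, the tables lose nothing and only the wording is at fault.

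A reader might multiply 1/46 by an assumed one to three subjects and report a loss of roughly 2 to 7 points. No count of affected subjects appears in the documents, so that range has no basis. The overall any-TEAE line is also unlikely to move much: the two dosing groups of Study 2009-003 had rates of 96.0% and 100.0% (protocol 1.4.1). Any effect would show, if at all, in individual terms or in the severity tables.

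**What to change.** In SAP 7.6.1, replace the words *during treatment* in the worsening sentence with the protocol 10.3.3 window, so that an AE present before first dose counts if it "subsequently worsens in severity between the first dose of study treatment and 30 days after the last dose of study treatment". If the shorter window was intended, record it as a departure with a reason, as SAP Section 1 requires. It would also help to state whether a grade change is entered as a new AE record.

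The cost is one phrase, and no new data are needed because AEs are already collected through 30 days after last dose. Amendment 4 describes the primary analysis and abbreviated report as complete, so the practical step may be to confirm which window was programmed, rerun the TEAE tables if it was the shorter one, and note the outcome in the report.
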